Estimated Total Drug Supply for Study: (number of tablets, capsules, vials)	10mg po qday (or placebo) for the first week and 10mg po qday (or placebo) for the final taper week (this means 14 days total taking 10mg tablets for 80 subjects = 1120 tablets [560 10-mg tablets and 560 placebos]) and 20mg po day for 11 weeks for 80 subjects (means 3080 tablets and 3080 placebos)
Total # of Subjects:	80 subjects (40 assigned to vortioxetine and 40 assigned to placebo)

Study Timeline:	
Planned Study Activation: (month/year)	September 1, 2015
Study activation is final regulatory authority approved protocol and fully executed contract	
Study Activation to First Patient In (days, weeks, months):	September 7, 2015 (within one week of study activation)
First Patient In to Last Patient In (days, weeks, months)	20 months
Last Patient In to Last Patient Out (days, weeks, months)	13 weeks
Monthly enrollment rate: (days)	4 subjects per month
Treatment duration: (in months)	3 months (12 weeks of treatment and 1 week taper off)
Number of Study Sites/Depots: (depots are defined as shipment facilities for sites)	1
Completion of Data Analysis: (# months)	2 months
Completion of Final Study Report/Manuscript: (month/year)	October, 2017
Publication Plan: (target journal, target conference)	American Journal of Psychiatry ACNP

STUDY PROPOSAL

Background

Binge-eating disorder recently included in the DSM-5, is now recognized as a serious public health problem (Kessler et al., 2013). Binge-eating disorder is associated with obesity and psychiatric comorbidities, including depression, and may be predictive of metabolic syndrome (Mathes et al., 2009). Many patients are undertreated despite functional impairments and personal and social difficulties leading to a poor quality of life (Hudson et al., 2007). Binge-eating disorder is characterized by recurrent episodes of excessive food consumption accompanied by a sense of loss of control and psychological distress but without the inappropriate compensatory weight-loss behaviors of bulimia nervosa. Binge eating is seen in 23–46% of obese individuals seeking weight loss treatment and its severity relates to body mass index and predicts regain of lost weight.

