Rationale for evaluating this compound in this population/target organ. Provide overall reason the study is being proposed, including past study results that may have led to a decision to propose this study.

Vortioxetine has distinctive properties that make it a promising option for patients with

binge eating disorder. In vitro studies indicate that vortioxetine is an inhibitor of the 5-HT transporter and is a 5-HT1D, 5-HT3 and 5-HT7 receptor antagonist, a 5-HT1A receptor agonist and a 5-HT1B receptor partial agonist. Animal and in vitro studies indicate that several neurotransmitter systems may be impacted by vortioxetine, with the drug enhancing levels of 5-HT, noradrenaline, dopamine, acetylcholine and histamine in certain areas of the brain, as well as modulating γ -aminobutyric acid and glutamate neurotransmission (Gibb and Deeks, 2014). In addition, vortioxetine appears to improve executive functioning which in turn has the potential to improve top-down cognitive control (Mahableshwarkar et al., 2015). This suggests that vortioxetine could improve the symptoms of binge eating disorder by two complementary pathways. Finally, because of low rates of side effects, low likelihood of sexual dysfunction, and the potential for improved cognitive performance, vortioxetine should be a well-tolerated and in fact desired medication approach to binge eating.

Given the serious public health problems associated with binge eating disorder, and the likelihood of success of vortioxetine in treating the disorder, the aim of the present study was to examine the efficacy and safety of vortioxetine vs placebo in adults with moderate to severe Binge eating disorder, as indicated by at least 3 binge eating days per week for the 2 weeks before the baseline visit

Hypothesis:

State hypothesis for study objectives.

We hypothesize that vortioxetine will be more effective than placebo in reducing the number of binge eating days per week after 12 weeks of treatment when compared to baseline.

Primary Aim/Objective:

For clinical studies– eg, To evaluate the safety and efficacy of interventions with test medication on symptoms, signs and quality of life in patients with target condition.

The aim of the present study is to examine the efficacy and safety of vortioxetine vs placebo in adults with moderate to severe Binge eating disorder, as indicated by at least 3 binge eating days per week for the 2 weeks before the baseline visit.

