Weight will be recorded using a calibrated scale with the participants not wearing shoes, rounded to the nearest 0.5 pounds, and converted to kilograms (to convert, multiply by 0.45) for data reporting.

Following-Up Visit Assessments

All follow-up visits will include safety measures (adverse events, vital signs, C-SSRS), weight, binge eating measures, Clinical Global Impressions–Improvement Scale, and other psychiatric measures.

Medical evaluation including physical examination will be performed again at study endpoint.

At study completion, participants will be made aware of all available options for follow-up care in the community.

Safety Assessments

Safety and tolerability will be assessed using spontaneously reported adverse events data, Columbia–Suicide Severity Rating Scale (C-SSRS) vital signs, and by evaluating premature termination. Safety assessments (C-SSRS, sitting blood pressure, heart rate, adverse effects, and concomitant medications) will be documented at each visit.

Subjects who are an immediate suicide risk will be removed from the study and appropriate clinical intervention (e.g. hospitalization) will be arranged. Urine pregnancy tests will be performed at the initial visit. Subjects who have a positive urine pregnancy test will be excluded from the study. Assessment of side effects will be done at each visit. AEs will be coded by system organ class (SOC) and preferred term (PT) using the Medical Dictionary for Regulatory Activities (Med- DRA) Version11.1. The incidences of all AEs will be summarized descriptively.

Safety Reporting (please do not change the safety section of the template)

Institution/Investigator is solely responsible for reporting all Adverse Events and Serious Adverse Events to regulatory authorities, investigators, IRBs or IECs and Takeda, as applicable, in accordance with national regulations in the countries where the study is conducted.

Regardless of expectedness or causality, all SAEs and pregnancy reports must also be reported in English by facsimile to Takeda Pharmacovigilance or designee:

Fatal and Life Threatening SAEs within 24 hours of the sponsor-investigator's observation or awareness of the event

All other serious (non-fatal/non-life threatening) events within 4 calendar days of the sponsor-investigator's observation or awareness of the event

Takeda Safety Reporting Contact Information

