Between group comparisons will use a mixed-effects model for repeated measures, including fixed factors for treatment and visit, the interaction of treatment and visit, a covariate of the log-transformation ([baseline number of BE days per week] + 1), and the interaction of the baseline covariate and visit using visit as a categorical variable. Mixed-effects models for repeated measures estimates differences from placebo in the change from baseline of the log-transformed scale ([BE days per week] + 1) at week 12 (primary end point). Based on previous research, log-transformation should reduce skewness (McElroy et al., 2007).

Secondary endpoints analyses

Secondary outcome measures will include the change from baseline in frequency of binge days (or mean days per week when the participant had one or more binges), weight, body mass index, global improvement, Three-Factor Eating Questionnaire, and Impact of Weight on Quality of Life.

We will also analyze changes from baseline in log-transformed BE episodes, TFEQ factor scores, and YBOCS-BE total score to week 12 using the mixed-effects model for repeated measures. Pairwise χ^2 statistical tests will evaluate dichotomized CGI-I ratings at week 12 for placebo vs treatment group.

Response categories will be tabulated based on the percentage decrease in frequency of binges from baseline to endpoint, which will be defined as follows: complete=cessation of binges; marked=75% to <100% decrease; moderate=50% to <75% decrease; and none=<50% decrease.

We will calculate effect sizes for the primary analysis of binges per week and weight using Cohen's d. Finally, we will perform a Spearman rank correlation to assess the association between the change in frequency of binges from baseline to week 12 and the change in weight from baseline using completers.

Safety analyses

Adverse events will be collected at baseline visit. We will evaluate differences between groups in the incidence of treatment-emergent adverse events using Fisher's exact test. Descriptive statistics will be used to evaluate changes in laboratory values, blood pressure and heart rate.

Sample Size

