The sample size was calculated for the primary endpoint of change from baseline in binge eating days per week. For 80% power to compare the change from baseline in binge eating days per week on the log-transformed scale, assuming an effect size of 0.6 to 0.7 between treatment group and the placebo group, 40 participants will be needed in each treatment group based on a 2-group t test at the .05 level of significance. Given the particularly low rates of adverse events reported with Vortioxetine, as well as its more positive side effect profile in terms of sexual side effects compared to other antidepressants used in binge eating disorder, we expect few drop-outs from the study and therefore a smaller sample is needed.

Feasibility

Given our past experience and the pacing of the study, we feel the goal to enroll 80 subjects in 20 months is practical and attainable. Given no-shows and rescheduling, and the time required for recruitment, telephone and in-person screening, and related issues inherent in any human study, the current goal of averaging at least 4 subjects per month is reasonable based on the fairly high prevalence of binge eating disorder, the number of subjects calling our outpatient clinic, and the large recruitment area of metropolitan Chicago. We will also employ our standard participant friendly provisions, including scheduling sessions in late afternoon/early evening and weekends, incorporating technological advances for contacts and reminders, and providing adequate compensation for participants' time.

Data Management Plan:

Data collected will consist of demographic data, subjective (self-report questionnaires, interview responses, ratings), and physiological (weight, heart rate and blood pressure). Access to individually identifiable private information about human subjects will be limited to Drs. [name] and [name] and their staff and will be collected specifically for the proposed research project. All collected data will be stored utilizing a 4-digit subject identification code, linked to separately stored identifying information via a coded log

only available to the PIs.

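### Safety is part of the primary aim, but the only planned between-arm statistic for adverse events is a Fisher's exact test; risk differences with 95% confidence intervals would be more informative at 40 per arm

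*Combined protocol and SAP*

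**What the plan says.** **Aim.** Primary Aim/Objective puts safety beside efficacy: "The aim of the present study is to examine the efficacy and safety of vortioxetine vs placebo in adults".

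**AE analysis.** Two places describe it.
- Safety Assessments: "The incidences of all AEs will be summarized descriptively".
- Statistical Analysis, Safety analyses: "We will evaluate differences between groups in the incidence of treatment-emergent adverse events using" Fisher's exact test. The same paragraph continues: "Descriptive statistics will be used to evaluate changes in laboratory values, blood pressure and heart rate".

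**Other safety measures.** Safety Assessments also lists the C-SSRS, vital signs and tolerability judged "by evaluating premature termination". Safety analyses says nothing about the C-SSRS or premature termination.

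**AE collection.** Safety analyses opens with "Adverse events will be collected at baseline visit" and names no other visit. Following-Up Visit Assessments puts AEs, vital signs and C-SSRS at all follow-up visits. Safety Assessments has side effects assessed at each visit.

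**Size.** The total is "80 subjects (40 assigned to vortioxetine and 40 assigned to placebo"). Sample Size derives this from efficacy alone: "40 participants will be needed in each treatment group based on a 2-group t test at the .05 level of significance". No safety hypothesis, margin, AE rate, significance level for the Fisher tests or interval for AE differences is given.

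**The concern.** A p-value answers one question: whether the data are incompatible with equal rates. A reader who wants to examine safety in a small trial has a different question: how large an excess the data show, and how large an excess they leave open. The plan provides for this on the efficacy side, with model-estimated differences from placebo and Cohen's d. It does not do so for AEs.

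The gap matters most for uncommon events. There, Fisher's exact test at 40 per arm rarely reaches significance even when the true rate is two or three times higher on drug. A table of p-values would then tell the reader little, and it would not show how wide the uncertainty is.

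Premature termination deserves a planned summary for a reason specific to this trial. Dose reductions are not permitted, and participants who cannot tolerate treatment are discontinued. Discontinuation is therefore one of the main places where poor tolerability would show.

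**Working it through.** **Inputs from the documents.** 40 per arm, 1:1. The safety-analysis set requires at least one dose and one follow-up safety assessment, so it has at most 40 per arm. The 0.05 level is stated for the efficacy t test only.

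**Assumptions.** Two-sided 0.05 for the Fisher tests. All AE rates below are assumed, because the documents give none.

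**Step 1. The plan's own figure.** Normal approximation: n per arm = 2(z₀.₉₇₅ + z₀.₈₀)²/d² = 2(1.960 + 0.842)²/d².
- d = 0.60 gives 44 (45 with the exact t test).
- d = 0.65 gives 38 (39).
- d = 0.70 gives 33 (34).

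Forty per arm lies inside the range for the stated effect sizes of 0.6 to 0.7. It reproduces as an efficacy figure. No safety quantity enters it.

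**Step 2. Power and size of Fisher's test.** Power = Σₓ Σᵧ Bin(x; 40, p₁) · Bin(y; 40, p₀) · 1[Fisher p(x, y) ≤ 0.05], summed over all 41 × 41 tables.

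| Active vs placebo (assumed) | Power |
|---|---|
| 10% vs 5% | 4% |
| 15% vs 5% | 18% |
| 20% vs 5% | 41% |
| 20% vs 10% | 16% |
| 25% vs 10% | 33% |
| 30% vs 10% | 53% |
| 40% vs 20% | 41% |
| 45% vs 15% | 79% |
| 60% vs 30% | 72% |

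With equal rates of 10%, the real type I error is 1.7% against the nominal 5%, so the test is conservative. For 80% power the active-arm rate must be about 29% if placebo is 5%, and about 38% if placebo is 10%. With 36 per arm (an assumed 10% loss), the 29% becomes 31%.

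**Step 3. What the interval adds.** Newcombe's interval combines the Wilson limits (l, u) of the two arms. With d = p₁ − p₀:

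lower = d − √[(p₁ − l₁)² + (u₀ − p₀)²]; upper = d + √[(u₁ − p₁)² + (p₀ − l₀)²].

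- *4/40 vs 4/40.* Wilson limits are 0.040 and 0.230 in each arm, and d = 0. Half-width = √[(0.100 − 0.040)² + (0.230 − 0.100)²] ≈ 0.144. Fisher p = 1.0; interval −14 to +14 points.
- *5/40 vs 0/40.* Wilson limits are 0.0546 to 0.2611 and 0 to 0.0876; d = 0.125. Lower = 0.125 − √[0.0704² + 0.0876²] = 0.013; upper = 0.125 + √[0.1361² + 0²] = 0.261. Fisher p = 0.055; interval +1 to +26 points.
- *9/40 vs 3/40.* d = 0.15; Fisher p = 0.115; interval −1 to +31 points.

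**Step 4. Coverage of the named safety measures.**

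| Measure in Safety Assessments | Analysis in Safety analyses |
|---|---|
| Adverse events | Fisher's exact test |
| Blood pressure, heart rate | Descriptive statistics |
| C-SSRS | None stated |
| Premature termination | None stated |

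**The case against.** **The two AE statements do not contradict each other.** A reader might infer that Safety Assessments restricts AEs to description while Safety analyses tests them. The documents do not support that: nothing in Safety Assessments says description is the sole treatment. It covers all AEs, the Fisher test covers treatment-emergent ones, and both can be done. This stands.

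**The plan never infers safety from a non-significant result.** A reader might assume that it does. The stated aim is to examine safety, Study Plan calls the trial a pilot, and there is no safety hypothesis or margin. Low power for AEs follows from the trial's size and does not make Fisher's test a wrong choice. This also stands. The point is only that a more informative summary is available.

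**The power figures depend on assumed rates.** True, and for commoner events power is moderate: 72% for 60% vs 30% and 79% for 45% vs 15%. The weakness is clearest for uncommon events and cannot be stated for all.

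**Incidences tabulated by arm would give the risk difference by subtraction.** True. What would still be missing is its uncertainty.

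**Intervals do not reverse the result.** At 9/40 vs 3/40 the interval also includes zero. At 5/40 vs 0/40 it excludes zero while Fisher's p is just above 0.05, but the two methods are not inversions of each other and Fisher's test is conservative. That example should not be read as proof of harm. The gain is in showing the range of compatible differences.

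**The baseline-visit sentence is a drafting slip.** Agreed. Study Plan, Following-Up Visit Assessments and Safety Assessments all place safety measures at later visits, and a treatment-emergent analysis requires it. There is little risk that on-treatment events go uncollected.

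**Conclusion.** The concern holds as an inexpensive improvement to the safety analysis; it does not show an error that invalidates the plan. Safety is in the primary aim, and the one stated between-arm statistic for AEs is a test that detects a tripling from 5% to 15% only 18% of the time and a tripling from 10% to 30% only 53% of the time. Identical counts of 4/40 still leave differences of up to 14 points open in either direction, which a p-value of 1.0 does not show.

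These figures rest on two-sided testing at 0.05, the full 40 per arm, and AE rates assumed for illustration. Fewer evaluable participants would lower power somewhat.

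Two smaller gaps come directly from the text and need no assumption: C-SSRS and premature termination are named as safety measures without a stated analysis, and the AE collection sentence in Safety analyses does not match the visit schedule elsewhere.

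**What to change.** In Statistical Analysis, Safety analyses:

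1. Make the between-arm risk difference with a 95% confidence interval (Newcombe or a similar score-based method) the main comparison for treatment-emergent AEs.
2. Give the same summary for premature termination and for post-baseline C-SSRS events.
3. Keep the Fisher p-values, labelled exploratory.
4. Reconcile the sentence on AE collection at the baseline visit with collection at each visit in Safety Assessments.

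The cost is a few sentences and a slightly longer safety table. All the data are already to be collected, and the sample size and the efficacy analysis are unaffected.

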Secondary Aim/Objective: *(if applicable)*

A secondary aim of the study is to examine the effects of vortioxetine vs placebo on overall functioning and quality of life.

Primary Endpoint(s):

The primary efficacy measure is the number of binge eating days per week based on clinician interview and confirmation of identified Binge eating episodes in self-reported Binge eating diaries. The primary efficacy end point is the change from baseline to week 12 on the log-transformed scale (Binge eating days per week) + 1.

Secondary Endpoint(s): (if applicable)

Secondary efficacy measures include the number of Binge eating episodes per week, 1-week Binge eating episode response status, and 4-week cessation from Binge eating (free from Binge eating episodes). Other secondary endpoints include the change in weight/BMI between baseline and study endpoint, the Clinical Global Impressions–Improvement Scale (CGI-I) rated global improvement of symptoms over time (results will be dichotomized as improved [CGI-I ratings of 1 or 2 very much/much improved] or not improved [CGI-I ratings of 3-7]). The self-reported Eating Inventory, also known as the Three-Factor Eating Questionnaire, the self-reported Binge Eating Scale, the Yale-Brown Obsessive Compulsive Scale modified for Binge Eating (YBOCS-BE), the Quality of Life Inventory, the Hamilton Depression Rating Scale and the Hamilton Anxiety Rating Scale.

Study Plan:

Eighty individuals with binge eating disorder will be recruited for a double-blind, placebo-controlled pilot study in which Vortioxetine or placebo is administered in a 1:1 fashion. All 80 subjects will have binge eating disorder per DSM-5 criteria for at least a year. Following baseline measures, subjects will receive Vortioxetine (10mg for one week and then 20mg thereafter) or inactive placebo. Participants will be seen one week after the baseline visit (assessing the 10mg dose), one week after that (assessing the 20mg dose), and then every 2 weeks for the remainder of the 12-week period. At week 12, subjects will start a 1-week taper off the medication and will be seen at week 13. Efficacy and safety measures will be performed at each visit.

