
Drugs, Dosages, and Regimens

Baseline visit will consist of all evaluations. For subjects who meet inclusion/exclusion criteria, they will be randomized at the end of their baseline visit.

All 80 subjects who are randomized to Vortioxetine (1:1 randomization) will receive 10mg/day or placebo during the first week of the study (the first dose will be started the day immediately after the baseline visit). All subjects will receive 10mg or placebo for 7 days and then will be evaluated with all measures at week 1 (7 days after baseline).

At the week 1 visit, subjects will be started on 20mg/day (or remain on placebo) for the remainder of the study. They will return at week 2 (corresponding to having been on 20mg/day for one week) and be evaluated with all measures. After week 2 visit, all subjects will be seen every two weeks for the remainder of the 12-week study period (this corresponds to visits at week 4, 6, 8, 10, and 12). Week 12 evaluation will be the study endpoint for purposes of efficacy.

All visits are as outpatients and include in-person assessments.

After study conclusion (at week 12), the dose will be tapered off during a 1-week follow-up period. All subjects will return at week 13 for final safety evaluation only.

Dosage changes/reductions will not be permitted. Because nausea, and possibly headache, are the most likely side effects anticipated at the 20mg dose, participants will be allowed the use of over-the-counter options such as Tylenol prn for headaches, or bismuth subsalicylate for nausea. The use of over-the-counter options will be tracked at each visit. If side effects continue and are intolerable, the participant will have to discontinue treatment. If that occurs, a detailed 'final visit' assessment will be conducted and the participant will be contacted two weeks following to assess side effect outcomes.

Treatment Duration, Visit Frequency, and Procedures

This is a 13-week study (12 weeks of acute treatment followed by a 1-week tapering phase). Subjects will be seen for a total of 9 study visits. All visits will include the full battery of assessments except week 13 which is only a safety evaluation.

Randomization

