A medication error is a preventable event that involves an identifiable patient and that leads to inappropriate medication use, which may result in patient harm. While overdoses and underdoses constitute medication errors, doses missed inadvertently by a patient do not. Individuals who identify a potential medication error situation should immediately contact Takeda (see below) and report the event.

Phone: [name] ([name])

E-mail: [contact]

[contact]

Product complaints and medication errors in and of themselves are not AEs. If a product complaint or medication error results in an SAE, an SAE form should be completed and sent to Takeda Pharmacovigilance.

Statistical Analysis:

Design/Randomization

The study is a double-blind, placebo-controlled study. Participants will be randomized (1:1) to receive vortioxetine or placebo by the University of Chicago Investigational pharmacy in block sizes of eight, using computer-generated randomization with no clinical information.

Efficacy Analysis

For statistical analysis, the full-analysis set will be defined as all participants who took at least 1 dose of the study drug and had at least 1 post-baseline primary efficacy assessment. The safety-analysis set will be defined as all randomized participants who took at least 1 dose of the study drug and completed at least 1 follow-up safety assessment.

We will compare the baseline characteristics of both groups using Fisher's exact test for categorical variables and the t test for continuous variables. We will calculate adherence to treatment, based on the number of capsules returned at each visit, as the number of capsules taken divided by the number of days in the study \times 100%.

Primary endpoint analysis

The primary outcome measure will be the change from baseline in frequency of binge eating episodes (binges/week), defined as the mean number of binges per week in 2-week intervals. If the visit interval is less than 2 weeks, the mean number of binges per week will be estimated based on the number of binge days in the interval since the last visit.

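### The stated 80% power with 40 per group does not hold at 0.6, the lower end of the plan's own effect-size range, where the sizing test (taken as two-sided) gives 75.5%

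*Combined protocol and SAP*

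**What the plan says.** The Sample Size section sizes the trial on the change from baseline in binge eating days per week, log-transformed, for 80% power, "assuming an effect size of 0.6 to 0.7 between treatment group and the placebo group, 40 participants will be needed in each treatment group". The calculation is "based on a 2-group t test at the .05 level of significance". The section does not say whether the test is one-sided or two-sided, or which value between 0.6 and 0.7 produced the 40. On attrition it says only that "we expect few drop-outs from the study and therefore a smaller sample is needed", with no rate.

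Three other places bear on the point:

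- **Primary endpoint analysis.** The planned analysis is not the t test: "Between group comparisons will use a mixed-effects model for repeated measures", with the log-transformed baseline as a covariate.
- **Design/Randomization.** Allocation is 1:1 "in block sizes of eight, using computer-generated randomization with no clinical information".
- **Study Plan.** Eighty people "will be recruited for a double-blind, placebo-controlled pilot study".

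**The concern.** A required sample size falls as the assumed effect grows, so a single number per group cannot give exactly 80% power at both 0.6 and 0.7. A reader who sees one power beside a range will naturally take it to hold across the range, including its least favourable point. If it does not, the plan overstates its chance of detecting an effect that it treats as plausible. At 0.6 the chance of missing a true effect would be 24.5% (100 − 75.5) instead of the 20% implied. A non-significant result could then be read as stronger evidence against an effect of 0.6 than the design supports.

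**Working it through.** **Inputs.** From Sample Size: 40 per group, effect size d from 0.6 to 0.7 (read as a standardised mean difference, because no separate difference or SD is given), two-group t test, level .05, target power 80%. From Design/Randomization: 1:1 allocation. Assumed: two-sided test. No drop-out is applied.

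**Formula.** With n per group, the t statistic has 2n − 2 degrees of freedom and noncentrality d × √(n/2). Power is the probability that this noncentral t falls beyond the two-sided .05 critical value.

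**Step 1: can the plan's 40 be reproduced?** Smallest n per group for 80% power:

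| d | n per group | Power at that n | Power at n − 1 |
|---|---|---|---|
| 0.60 | 45 | 80.4% | 79.5% |
| 0.65 | 39 | 80.9% | 79.9% |
| 0.70 | 34 | 81.2% | 80.0% (79.97%, just under) |

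At d = 0.64 exactly 40 are needed. The plan's 40 is therefore reproduced near the middle of the range. It also fits the blocking, since 80 / 8 = 10 complete blocks. It is reproduced at neither end.

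**Step 2: power with 40 per group.** Here there are 2 × 40 − 2 = 78 degrees of freedom, the critical value is 1.991, and √(40/2) = 4.472.

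| d | Noncentrality (d × 4.472) | Power |
|---|---|---|
| 0.60 | 2.683 | 75.5% |
| 0.65 | 2.907 | 81.9% |
| 0.70 | 3.130 | 87.1% |

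Solving for exactly 80% gives d = 0.634. The part of the range below 80% is (0.634 − 0.600) / (0.700 − 0.600), about one third. The gap at 0.6 is 80 − 75.5 = 4.5 points. The normal approximation gives nearly the same answer: 76.5% at 0.6, and 80% at 0.626.

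**Step 3: would a one-sided test explain the statement?** At one-sided .05, 40 per group gives 84.5% at 0.6, so 80% would hold throughout. But that test needs only 36, 30 and 26 per group at 0.6, 0.65 and 0.7. It does not lead to 40 anywhere in the range.

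**Step 4: what might the planned model add?** As an approximation, take a single-time-point analysis adjusted for baseline. Let k be the baseline SD divided by the week-12 SD and r their correlation. The change score has variance proportional to 1 + k² − 2kr, and the adjusted analysis has residual variance proportional to 1 − r². An effect of 0.6 on the change score becomes 0.6 × √[(1 + k² − 2kr) / (1 − r²)]. The values of k and r below are assumptions; the plan gives none.

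| k | r | Adjusted effect | Power, 40 per group |
|---|---|---|---|
| 1.0 | 0.5 | 0.693 | 86.4% |
| 1.0 | 0.7 | 0.651 | 82.0% |
| 1.0 | 0.8 | 0.632 | 79.8% |
| 0.8 | 0.3 | 0.677 | 84.9% |
| 0.8 | 0.5 | 0.635 | 80.1% |
| 0.6 | 0.5 | 0.604 | 76.0% |

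The gain runs from about half a point to about 11 points, depending on inputs that the plan does not state.

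**The case against.** The best defence is that 40 is not a miscalculation. A single sample size beside a range is fairly read as planned near the centre, where power is 81.9%, and the section never says outright that 80% holds at every point. That stands as far as the number 40 goes. It does not rescue the sentence, which ties 80% to the whole range and names no planning value.

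The second defence is that the trial will be analysed with a baseline-adjusted model, which under many plausible inputs brings power at 0.6 to 80% or more. This too is partly right, and it limits what can be claimed: the 4.5 points describe the sizing test, not the planned analysis. But the section rests its power on the t test, and the model's gain could be negligible, so it cannot be credited on the plan as it stands.

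Two stronger readings are tempting and should be resisted.

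- **That the sample size is wrong or the trial underpowered.** The documents do not support this. The 40 fits the middle of the stated range, and the Study Plan calls the trial a pilot.
- **That drop-out pushes real power well below 75.5%.** Some stopping is foreseen: under Drugs, Dosages, and Regimens, "If side effects continue and are intolerable, the participant will have to discontinue treatment". But no loss rate is given, and the expectation of few drop-outs points to little or no inflation in the 40. The full-analysis set under Efficacy Analysis keeps anyone dosed who has at least one post-baseline primary assessment, and the repeated-measures model uses partial records. Treating every early stopper as lost would overstate the damage. All that can be said is that 75.5% is a figure before drop-out.

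**Conclusion.** Wrong as written, and minor. On the plan's own t test, taken as two-sided at .05 with 40 evaluable participants per group, the claimed 80% holds from an effect size of about 0.634 upward. It fails over roughly the lower third of the range, by at most 4.5 points, at 0.6. Reaching 80% there would take 45 per group, or 90 in total, before any allowance for loss. The conclusion depends on the two-sided reading; under a one-sided .05 test the power claim would hold, though 40 would then be more than is needed. Whether the planned mixed model closes the gap cannot be determined from the documents.

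**What to change.** Keep 80 participants and rewrite the power statement in Sample Size so that it is tied to a named effect size. For example:

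> 40 participants per group give about 82% power at an effect size of 0.65 (75.5% at 0.6, 87% at 0.7; 2-group t test, two-sided .05, before drop-out).

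The sponsor should confirm the planning value actually used (0.65 is inferred here from the arithmetic) and that the test is two-sided. If the sponsor prefers to claim 80% at 0.6 through the mixed model, the section would need to state the baseline-to-week-12 correlation and the two SDs behind that claim.

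The cost is wording only: no extra participants and no change to design or analysis. The one downside is that the stated power looks slightly less favourable at 0.6.
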